
Study Objectives

Primary Objectives

The **primary objective** of this study is to evaluate the current management approach with “intermediate” or “therapeutic” doses of tinzaparin for thromboprophylaxis in hospitalized patients, non on ICU organ support, with confirmed COVID-19.

- Evaluate incidence of thrombotic events
- Evaluate incidence of bleeding events

Secondary Objectives

The **secondary objective** is to

- ✓ Examine the course of illness of COVID-19 via measure of clinical improvement and/or survival, assessed at pre-specified time points post admission

Patients demographic & somatometric data, medical history (thrombosis & bleedings related history, co-morbidities, chronic use of medications, results of laboratory tests etc.), clinical parameters, anticoagulant prophylaxis dose & duration, efficacy (thrombosis events), safety (bleedings), imaging and laboratory tests results and information about other supportive treatment will be recorded; more than one outcomes could be recorded.

Based on analysis of collected data, **we'll examine correlations between thromboprophylaxis approach, patients' profiles and clinical outcomes.**

Study Endpoints

Primary Endpoints

- **Incidence of thrombotic events** (total & per type e.g. PE, DVT, symptomatic, incidental, proximal, distant etc.)
- **Incidence of bleeding events** (total & per type e.g. Major, CRNMB and minor)

Secondary Endpoint

- **World Health Organization (WHO) progression scale** (range from 0 (healthy) to 10 (death); values below or equal to 5 correspond to the absence of any oxygen supply beside nasal or facial mask)
- **Length of hospital stay (days)**

Study Design

This is a retrospective phase IV, observational, non-interventional cohort study that aims to collect data regarding thromboprophylaxis management in high thrombotic risk hospitalized, non on ICU, patients with COVID-19 pneumonia. Specifically, we will collect retrospectively data for patients received thromboprophylaxis with tinzaparin, according to current clinical practice, during hospitalization, for one year before the study initiation date, to evaluate safety and efficacy of thromboprophylaxis and to examine possible associations of

patients' profiles with thrombotic and bleeding events and the course of illness in this cohort of patients.

We will collect data retrospectively in paper CRFs, recorded from the treating physicians.

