Additionally, we will assess the association of a panel of laboratory and clinical parameters representing an inflammatory and hemostatic state with VTE and bleeding events and clinical outcomes.

Institutional Review Board will approve the study.

Basic/common markers/parameters

- ✓ *D-Dimers*
- ✓ *C-reactive protein (CRP)*
- ✓ *hemoglobin*
- ✓ *platelets count*
- ✓ *ferritin*
- ✓ *fibrinogen*
- ✓ *SpO₂ in FiO₂ 21%*

In all cases, laboratory and clinical parameters will be collected at 3 time points: at admission/baseline, after one week and at discharge.

Subject Population

Key criteria for Inclusion and Exclusion

Inclusion Criteria

1. Patients admitted to hospital with COVID-19, PCR+ SARS-CoV-2 infection (from any specimen) administered thromboprophylaxis with tinzaparin in intermediate or therapeutic dose
2. Age \geq 18 years
3. Signed informed consent

Exclusion Criteria

1. Patients admitted to ICU with COVID-19, PCR+ SARS-CoV-2 infection (from any specimen)
 2. Age < 18 years
 3. Pregnancy
 4. Current diagnosis or suspicion of pulmonary thromboembolism or deep vein thrombosis
 5. Progression to death was imminent and inevitable within 24 hours from the admission, irrespective of the provision of treatments
 6. Not signed informed consent
-

Study Phases**Screening**

(1) Screening: screening patient files for eligibility, obtaining consent, If eligible

All the data will be gathered from medical records by chart review of the individual patients in a retrospective fashion. There will no direct patient interaction in the study.

Data collection

- Demographic data collection (Gender, Date of birth, Weight, Height, etc.)
- Medical history & pathologic features (Thrombosis & bleedings related history, risk factors, recent surgery, co-morbidities, chronic use of medications, results of laboratory tests, clinical parameters etc.)
- Anti-coagulant administration data
- Thrombotic & bleeding events during course of hospitalization
- Other adverse events related to anticoagulation
- Clinical improvement and/or survival during hospitalization

Timepoints of evaluation

Data of Covid-19 pneumonia patients retrospectively enrolled in the study will be evaluated on a regular basis following the Baseline Visit;

Visit 1 – Baseline, at admission;

Visit 2 - will be after 1 week \pm 2 days

Visit 3 - will be by at discharge from hospital

Statistical analysis & report**Statistical analysis****Statistical and Analytic Plan**

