Descriptional statistical analysis will be performed for all study data along with epidemiology methods. Categorical data will be analyzed using the *chi-square* and *Fisher exact test*. Continuous variables will be reported as mean and standard deviations (SD) and will be analyzed using the *t-test* analysis. An unadjusted odds ratio (OR) will be calculated using a *Cochran-Mantel-Haenszel test*. To determine the impact of potential effect modifiers a *logistic regression model* will be used to calculate the adjusted odds ratio. For more complex correlations (i.e. inferential statistics) we will use, among other methods, *chi-square* or *Fisher exact tests*, *ANOVA*, *Mann-Whitney U tests* and *t-tests*, according to the data properties and in order to evaluate the relationships between different patient and disease characteristics with the primary and secondary study outcomes, such as:

- ✓ *Number of patients enrolled*
- ✓ *Co-morbidities*
- ✓ *Thrombosis risk factors*
- ✓ *Laboratory parameters*
- ✓ *Clinical parameters*
- ✓ *Type and duration of thromboprophylaxis therapy*
- ✓ *Therapy outcomes*
- ✓ *Thromboprophylaxis related complications*

and to present them, accordingly.

Due to the fact that this is an observational study the results of all correlations will be carefully discussed and will be used only to assess hypotheses.

Finally and depending on the collected data multivariate analysis may be performed in order to reveal confounding factors.

Clinical Study Report (CSR)

Analyzed parameters will be presented with standards statistical measures (mean values, median values, ranges, quartiles, percentages etc.) and the results will be presented accordingly into tables and informative plots.

A p-value of less than 0.05 will be considered statistically significant and all values will be reported with a 95% confidence interval (CI).

Study Registration

Study will be registered in

NIH, U.S. National Library of Medicine, Clinical Trials database of privately and publicly funded clinical studies, <https://clinicaltrials.gov/ct2/home>

Efficacy Evaluations

- ***Symptomatic/Suspected vein thromboembolism, including pulmonary embolism and deep vein thrombosis***

Confirmation of symptomatic PE requires symptoms of PE and one of the following findings

1. *A (new) intraluminal filling defect in (sub) segmental or more proximal branches on spiral CT scan or on MRI scan;*

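### Duration of prophylaxis is among the factors to be related to length of stay, but in-hospital treatment days are part of the stay, so a positive association is built in with no effect present

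*Combined protocol and SAP*

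**What the plan says.** Under Study Endpoints, length of hospital stay in days is listed as a secondary endpoint, beside the WHO progression scale.

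Under Statistical and Analytic Plan, the sponsor will use chi-square or Fisher tests, ANOVA, Mann-Whitney and t-tests, among other methods, to "evaluate the relationships between different patient and disease characteristics with the primary and secondary study outcomes". The list that follows includes "Type and duration of thromboprophylaxis therapy" and "Thromboprophylaxis related complications". Study Objectives says that "anticoagulant prophylaxis dose & duration" will be recorded and that the study will "examine correlations between thromboprophylaxis approach, patients' profiles and clinical outcomes".

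The time window is the hospital stay. Study Design describes "patients received thromboprophylaxis with tinzaparin, according to current clinical practice, during hospitalization". Data collection covers "Thrombotic & bleeding events during course of hospitalization", and the last timepoint, Visit 3, is discharge.

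The significance threshold is p<0.05. The plan says that correlations will be discussed with care and used only to assess hypotheses, and that a multivariate analysis may be done to reveal confounders. No text limits the factors to baseline values, and no landmark, person-time or time-dependent method is named.

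**The concern.** Days of in-hospital prophylaxis cannot exceed days in hospital. A patient discharged on day 5 has at most five days of treatment, while a patient discharged on day 20 can have twenty. Relating one to the other is a part-whole comparison and carries no information about what prophylaxis does to the course of illness.

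At stake is a secondary endpoint. The report could present a highly significant link between longer prophylaxis and longer stay that would have appeared under any treatment or none.

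A related problem arises only if total stay is also compared between patients with and without an in-hospital thrombosis or bleed. Patients who stay longer for any reason have more days on which to have an event, and the days before the event are counted as if they followed from it.

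**Working it through.** The documents state no sample size, event rate or stay distribution, so there is no figure of the plan's own to reproduce. All numerical inputs below are assumptions, shown over a range.

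**1. Duration against stay, closed form.** Let L be the stay and D = U × L the days of prophylaxis, where the share U is independent of L. Then Cov(D, L) = E[U] × Var(L), which is positive whatever the distribution of L. With c² = Var(L)/E[L]² and k² = Var(U)/E[U]²,

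r = √( c² / (c² + k²(1 + c²)) ).

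For a lognormal stay with log-SD s, c² = exp(s²) − 1. For U uniform from a to 1, k² = [(1 − a)²/12] / [(1 + a)/2]².

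| s | a | c² | k² | r |
|---|---|---|---|---|
| 0.4 | 0 | 0.1735 | 0.3333 | 0.55 |
| 0.8 | 0 | 0.8965 | 0.3333 | 0.77 |
| 0.6 | 0.5 | 0.4333 | 0.0370 | 0.94 |
| 0.6 | 0.8 | 0.4333 | 0.0041 | 0.99 |

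**2. Duration against stay, simulation with no effect.** Median stay was 7 or 10 days, with s from 0.4 to 0.8.

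- Prophylaxis as a random share of the stay (lower limit 0, 25, 50 or 80%): Pearson 0.56 to 1.00, Spearman 0.46 to 0.99. This agrees with the closed form.
- A planned course chosen independently of the stay and cut off at discharge: Pearson 0.45 to 0.54, Spearman about 0.60.
- Treatment started on day 0 to 2 (median stay 7 to 9 days, s 0.5 to 0.7): Spearman 0.98 to 0.99 if all are treated to discharge, 0.89 to 0.93 if 10% stop early, 0.76 to 0.82 if 30% stop early.
- Mann-Whitney test of stay by long versus short prophylaxis (median split, two-sided 0.05), over the first two models: p<0.05 in 81 to 100% of studies with N = 50 and in 98 to 100% with N = 100.

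**3. Stay by event status (conditional point).** Assume a constant daily event risk that does not change the stay. When events are rare, patients with an event have close to the length-biased mean stay, E[L²]/E[L], which is exp(s²) times the overall mean: 1.17 times at s = 0.4 and 1.90 times at s = 0.8. For median 10 and s = 0.6, the overall mean is 10 × exp(0.18) = 12.0 days and the length-biased mean is 10 × exp(0.54) = 17.2 days. The simulation with 5% events gave 17.0 days with an event and 11.7 without.

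Over event rates of about 2, 5 and 10%, the simulated ratio was 1.18 to 1.90. Mann-Whitney false-positive rates were:

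| N | p<0.05 with no effect |
|---|---|
| 100 | 5 to 62% |
| 300 | 13 to 97% |
| 1000 | 42 to 100% |

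The correlation coefficient stayed small (0.06 to 0.25) because events are rare. If all event risk falls in the first 3 days, the difference in mean stay is −0.01 to 0.37 days.

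**4. Effect of a landmark.** Events up to day 7 were compared on remaining stay, among patients still in hospital after day 7 (s = 0.6, 5 or 10% events, N = 300 or 1000). False positives were 4.3 to 5.3%, against 60 to 100% for total stay on the same data.

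**The case against.** The strongest objection is that no sentence pairs duration with length of stay. The list is loosely worded: it contains the number of patients enrolled, which is not a patient-level variable, and it mixes factors with outcomes. This stands as a limit on wording, since the pair is inferred. It does not remove the point, because duration is listed, length of stay is a secondary outcome, and nothing excludes testing one against the other.

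The plan also promises cautious discussion, and a statement that longer prophylaxis goes with longer stay would be true as description. That softens the harm. Caution does not make the p-value informative, however, and adjustment for confounders cannot undo a part-whole relation. The plan names no correlation coefficient, but the Mann-Whitney test that it does name gives the same result.

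The documents do not say whether prophylaxis after discharge would be counted. No visit or data item extends past discharge, so containment in the stay is the natural reading.

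A reader might go further and infer that the plan also makes thrombosis and bleeding predictors of stay, with strong and near-certain false associations. The documents do not support that. Complications appear in the list, but no sentence expressly proposes them as a factor for stay, and thrombosis and bleeding are primary endpoints. The size of any bias depends on a sample size and event rate that the documents do not give, and on risk continuing through the stay. A complication may also truly prolong the stay; a comparison of total stays cannot separate the two.

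**Conclusion.** The point holds for duration of prophylaxis. On the natural reading of the plan, one exploratory analysis of a secondary endpoint has its answer built in. The direction needs only that treatment days are counted within the stay, and a positive association appeared under every model tried. The coefficient depends on the assumed stay distribution and on how often treatment stops before discharge. A significant result is near-certain with 100 patients or more.

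The comparison by event status is a secondary point, conditional on that analysis being done. Its direction is clear if risk continues through the stay. Its size is not fixed by the documents and may be negligible if events cluster in the first days.

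The primary incidence estimates are not affected.

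**What to change.** 1. In the Statistical and Analytic Plan, state that duration of prophylaxis will not be tested against length of stay. Report it descriptively, in days and as a share of hospital days.
2. State that length of stay will be related only to characteristics fixed at admission or at the start of prophylaxis.
3. If length of stay is to be compared by thrombosis or bleeding, do not compare total stays. Choose a common hospital day in advance, classify patients still in hospital by events up to that day, and compare days remaining. This needs event dates. The documents do not say that dates are recorded, so confirm that the CRF captures them. Without dates, report stay by event status descriptively and without a test.

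Items 1 and 2 cost two sentences and lose only a correlation that carries no information. Item 3 costs a little programming and possibly one CRF field. Few patients will contribute events: at an assumed 5% rate, 300 patients give about 300 × 0.05 = 15 events before restriction to those still in hospital, so a simple landmark comparison is as much as the data are likely to support.

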2. *A (new) intraluminal filling defect or an extension of an existing defect or a new sudden cut-off of vessels on the pulmonary angiogram;*
3. *An inconclusive lung scan accompanied by documentation of (new) DVT in the lower extremities e.g., by compression ultrasound or venography.*

Confirmation of symptomatic DVT requires symptoms of DVT and:

1. *A (new) non-compressible venous segment on ultrasonography
Incidental PE with one of the following:*
2. *A (new) intra-luminal filling defect on CT scan, MRI scan, or pulmonary angiogram;*
3. *An inconclusive lung scan accompanied by documentation of (new) DVT in the lower extremities e.g., by compression ultrasound or venography.*

Fatal PE is:

1. *PE based on objective diagnostic testing or autopsy or*
-

-
2. *Death not attributed to a documented cause and for which DVT/PE cannot be ruled out*

Incidental DVT with the following finding:

Confirmation of incidental DVT requires inconclusive or no- symptoms of DVT and:

1. *A (new) non-compressible venous segment on ultrasonography*

**Safety Evaluations
(with regards to
anticoagulation)**

- **Major, Clinically Relevant Non-Major Bleeding (CRNMB), and minor bleeding**

Major bleeding will be defined as overt bleeding associated with: a fall in hemoglobin of 2 g/dL or more, or leading to a transfusion, or bleeding that occurs in a critical site or contributing to death.

- **Bleeding in a critical area or organ such as:**

- ✓ *Retroperitoneal*
- ✓ *Intracranial*
- ✓ *Intraocular*
- ✓ *Intraspinal*
- ✓ *Intra-articular*
- ✓ *Pericardial*
- ✓ *Intramuscular with compartment syndrome*

- **A clinically overt bleeding event**

- ✓ *that is associated with a fall in hemoglobin of 2.0 g/dL (>1.24 mMol/L) or more, or*
- ✓ *leading to a transfusion of ≥ 2 units of packed red blood cells or whole blood*

- **Bleeding contributing to death**

- Other **clinically relevant non-major bleedings (CRNMB)** will be defined as overt bleeding not meeting the criteria for major bleeding but associated with medical intervention, unscheduled contact (visit or telephone call) with a physician, (temporary) cessation of study treatment, or associated with discomfort for the patient such as pain, or impairment of activities of daily life.
 - All other bleeding events will be classified as **minor**
-

- **World Health Organization (WHO) progression scale**

Patient State	Descriptor	Score
Uninfected	Uninfected; no viral RNA detected	0

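### The symptomatic and incidental PE definitions have no criterion for a diagnostic lung scan, so a non-fatal PE shown only by a positive scan can be missed or classified inconsistently

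*Combined protocol and SAP*

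**What the plan says.** The first primary endpoint (Study Endpoints, Primary Endpoints) is the incidence of thrombotic events, reported "total & per type e.g. PE, DVT, symptomatic, incidental, proximal, distant etc". PE therefore enters both the overall count and a count of its own.

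The Efficacy Evaluations section defines the events:

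- **Symptomatic PE.** "Confirmation of symptomatic PE requires symptoms of PE and one of the following findings". Three findings follow: "A (new) intraluminal filling defect in (sub) segmental or more proximal branches on spiral CT scan or on MRI scan"; "A (new) intraluminal filling defect or an extension of an existing defect or a new sudden cut-off of vessels on the pulmonary angiogram"; and "An inconclusive lung scan accompanied by documentation of (new) DVT in the lower extremities e.g., by compression ultrasound or venography".
- **Incidental PE.** One of two findings: "A (new) intra-luminal filling defect on CT scan, MRI scan, or pulmonary angiogram", or the same inconclusive-scan criterion in the same words.
- **Fatal PE.** The first of two alternatives reads "PE based on objective diagnostic testing or autopsy or", and the second covers deaths without a documented cause in which DVT or PE cannot be excluded. The first does not restrict the type of test.
- **DVT, symptomatic or incidental.** "A (new) non-compressible venous segment on ultrasonography".

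The Study Design section has treating physicians record the data retrospectively on paper CRFs. The document describes no adjudication or central re-coding of events against these definitions.

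**The concern.** The two non-fatal PE lists accept lung scanning as a source of evidence, but only when the scan is inconclusive and a new DVT is documented. A scan that settles the diagnosis has no place in either list. If the authors had meant to exclude lung scanning they would have left it out altogether, so this looks like an omission. It leaves the definitions at odds with one another: a better scan earns a lesser classification, and the same positive scan can count as PE if the PE is fatal but not otherwise.

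Two things are at stake. If the rule is followed literally, some PEs drop out of the PE-specific incidence, and some of those also drop out of the total. If some physicians follow the rule and others record the chart diagnosis, like cases are coded differently. Either way the same event variable feeds the association analyses in the Statistical and Analytic Plan.

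**Working it through.** The plan states no sample size, expected incidence or imaging mix, so there is no figure of its own to reproduce. The check is a reading of the rules, followed by an illustration on assumed inputs.

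**Step 1: apply the rules.** Take a patient with no CT, MRI or angiogram finding. The result is the same under the symptomatic and the incidental list.

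| Lung scan | New leg DVT | PE fatal? | Counted as |
|---|---|---|---|
| Positive | None | No | Nothing |
| Positive | Ultrasound | No | DVT only |
| Positive | Venography only | No | Nothing: the DVT rules list only ultrasonography |
| Inconclusive | Ultrasound | No | PE and DVT |
| Positive | Any or none | Yes | Fatal PE |

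The second and fourth rows differ only in the quality of the scan, and the better scan loses the PE. The wording that introduces examples in the inconclusive-scan criterion concerns how the DVT is documented, so it does not open the list to other scan results. In the extracted text the incidental PE heading runs on from the DVT item and its numbering starts at 2. I treat that as layout, and the point about the symptomatic list does not depend on it.

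**Step 2: direction.** Adding a criterion can only add PEs, so its absence can only lower the PE count. The total, counted as patients with at least one event, falls only for patients with a positive scan, no other qualifying PE imaging, no ultrasound-confirmed DVT and no fatal PE.

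**Step 3: illustrative size.** All three inputs are assumptions:

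- p = share of patients with a thrombotic event who have a PE (0.4 to 0.9)
- s = share of those PEs that are non-fatal and rest only on a positive scan (0 to 20%)
- u = share of that group without an ultrasound-confirmed DVT (0.5 to 1.0)

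Relative loss in PE incidence = s. Relative loss in total incidence = p × s × u.

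| p | s | u | Loss in total | True 5% recorded as |
|---|---|---|---|---|
| any | 0 | any | 0% | 5.000% |
| 0.4 | 2% | 0.5 | 0.4 × 0.02 × 0.5 = 0.4% | 4.980% |
| 0.7 | 5% | 1.0 | 0.7 × 0.05 × 1.0 = 3.5% | 4.825% |
| 0.9 | 20% | 1.0 | 0.9 × 0.20 × 1.0 = 18% | 4.100% |

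If the total counts events rather than patients, every lost PE is a lost event, which is the case u = 1.0.

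**Step 4: scale against sampling error.** In an assumed cohort of 500 with 10 patients having events, losing one moves the estimate from 2.0% (Clopper-Pearson 95% CI 0.96 to 3.65) to 1.8% (0.83 to 3.39). The shift is small beside the interval, but it goes one way and more patients would not remove it.

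**The case against.** The strongest reply is that the plan shows a gap in wording and nothing about its effect. A reader might infer that the primary thrombotic incidence is understated. The documents do not support that. They report no lung-scan use, and if no PE rested on a positive scan alone the effect is zero. The fatal PE rule also counts some deaths of undocumented cause as PE, which pushes the other way, so the net direction of error in the reported endpoint is not shown. This stands.

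A reader might also state a definite percentage loss. That would only restate whatever share of scan-only PEs had been assumed. Or a reader might infer that the loss falls selectively on certain patients, such as those in whom contrast is avoided, and so distorts the associations. The plan does not describe imaging practice, and it limits the correlations to assessing hypotheses. Both inferences go beyond the text.

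Two further replies have some force. Physicians complete the CRFs, and one might record a scan-diagnosed PE regardless of the list. That turns certain loss into possible inconsistency; it does not remove the problem. It can also be said that a positive scan with DVT meets the inconclusive-scan criterion with something to spare. That is a sensible reading, but it is not what the rule says, and it does nothing for a positive scan without DVT.

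What survives is the gap itself. Two stated definitions omit a finding that the third would accept, and nothing else in the document admits it for a non-fatal PE.

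**Conclusion.** The point holds as a defect in the endpoint definition: wrong as written, of low to moderate severity. The conflict between the non-fatal and fatal PE rules follows from the text and needs no assumption. So does the direction of this one omission: down, if it has any effect, and felt first in the PE-specific incidence, because a positive scan with ultrasound-confirmed DVT keeps the patient in the total.

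The size cannot be obtained from the documents. The range of 0% to 18% relative loss in the total, and 0% to 20% in PE incidence, rests wholly on the assumed inputs, and nothing in the plan places the study within it. The supportable conclusion is that PE incidence, and to a lesser extent the total, may be lowered by an unknown and possibly zero amount, or that like cases may be coded differently by different physicians.

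**What to change.** In both the symptomatic and the incidental PE lists, add a criterion for a (new) lung scan reported as diagnostic of PE. Keep the inconclusive scan with new DVT as the fallback. Align the two lists with the fatal PE wording, so that the same test result is classified alike whatever the outcome. Apply the amended definition to all CRFs before any events are counted.

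The cost is one added line in each list and a small re-check of any CRFs already completed. The data come from existing charts, so no new procedure is needed. The CRF is not among the documents; if it does not record the scan result, a field would have to be added.

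### Both DVT definitions accept only an ultrasound finding, while the PE criteria also accept venography as proof of DVT, so the DVT part of the first primary endpoint may be undercounted or inconsistently classified

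*Combined protocol and SAP*

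**What the plan says.** Under Study Endpoints, the first primary endpoint is the incidence of thrombotic events, reported "total & per type e.g. PE, DVT, symptomatic, incidental, proximal, distant etc". DVT is therefore a named reporting class of a primary endpoint. The incidental class is named as well.

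Efficacy Evaluations holds the only event definitions:

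- **Symptomatic DVT:** "Confirmation of symptomatic DVT requires symptoms of DVT and" one finding, "A (new) non-compressible venous segment on ultrasonography".
- **Incidental DVT:** introduced in the singular, "Incidental DVT with the following finding". Then "Confirmation of incidental DVT requires inconclusive or no- symptoms of DVT and" the same ultrasound finding.
- **PE, symptomatic and incidental:** several alternative findings. One is an inconclusive lung scan together with "documentation of (new) DVT in the lower extremities e.g., by compression ultrasound or venography". For incidental PE another is "A (new) intra-luminal filling defect on CT scan, MRI scan, or pulmonary angiogram". Symptomatic PE has comparable CT, MRI and angiographic routes.

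No DVT criterion mentions venography, CT or MRI. On data source, Study Phases states: "All the data will be gathered from medical records by chart review of the individual patients in a retrospective fashion". Study Design adds that the treating physicians complete paper CRFs.

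**The concern.** The section applies two standards to the same diagnosis. A venogram is good enough to document a DVT when the DVT supports a PE, but not when the DVT is the event being counted. Beyond that contradiction, the DVT definitions have no CT or MRI route, whereas the PE definitions do. An unsuspected deep-vein thrombus on a CT done for another reason cannot meet the incidental DVT definition on that scan. An unsuspected PE on a CT can meet its own.

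Imaging was whatever routine care used, and the study involves no patient contact. An event documented in the chart by another modality cannot be given its ultrasound afterwards. The study describes how well thromboprophylaxis performed, so a rule that can only remove DVTs shifts that component in the favourable direction. If physicians do not all read the rule literally, the count depends on who abstracted the chart.

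**Working it through.** The plan gives no figure to reproduce: no sample size, expected DVT rate or imaging mix. The check is a comparison of the text, followed by an illustration on assumed numbers.

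**Step 1. Which evidence is accepted for which event (Efficacy Evaluations)**

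| Evidence | As DVT evidence within the PE criteria | As a DVT event, symptomatic or incidental |
|---|---|---|
| Compression ultrasound | Accepted, named | Accepted, the only finding listed |
| Venography | Accepted, named | Not listed |
| CT or MRI of a deep vein | Not named; the list of examples is open | Not listed |

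The venography row is an explicit contradiction. The CT and MRI row is an omission. It stands out because filling defects on those scans qualify as PE.

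**Step 2. Does the layout explain it?** In the document as read, the incidental PE line runs on from item 1 of the symptomatic DVT list, and the CT/MRI item follows as number 2. That item names the pulmonary angiogram and follows the incidental PE line, so it belongs to PE. The separate incidental DVT entry repeats the single ultrasound finding, so the point does not depend on the numbering.

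**Step 3. Direction and size for DVT.** Let D be the true number of DVTs and f the share documented only by a modality other than ultrasound and not recorded as DVT. Then

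counted DVT = D × (1 − f), and relative loss = f.

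Since f cannot be negative, this rule alone can only lower the DVT count. The value of f is not in the documents and may be zero.

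Illustration with assumed N = 500, D = 10 and f from 0% to 30% (Clopper-Pearson 95% intervals):

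| f | Counted DVTs | Incidence | 95% CI |
|---|---|---|---|
| 0% | 10 | 10/500 = 2.0% | 0.96% to 3.65% |
| 10% | 9 | 9/500 = 1.8% | 0.83% to 3.39% |
| 20% | 8 | 8/500 = 1.6% | 0.69% to 3.13% |
| 30% | 7 | 7/500 = 1.4% | 0.56% to 2.86% |

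The largest absolute loss in this range is 2.0 − 1.4 = 0.6 percentage points.

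**Step 4. Total thrombotic incidence.** With P other counted thrombotic events, such as PE, the relative loss in the total is at most

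f × D / (D + P),

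which is below f whenever P and f are above zero. It is an upper limit because a venography-proven DVT accompanied by an inconclusive lung scan can still enter the total as PE.

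**The case against.** The strongest reply is that loss is not certain. The primary endpoint is worded as thrombotic events, without saying that only confirmed ones count, and no adjudication is described. A treating physician may well record a venography-proven DVT. This stands, and it limits the claim: loss follows only if the definitions are applied as written. It does not remove the problem. One abstractor taking the word *requires* at face value excludes the event and another includes it, so the outcome is then inconsistent classification.

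The size may also be negligible. If nearly all DVTs were diagnosed by ultrasound, f is close to 0%. The percentages above restate an assumption, and even 1.4% lies inside the interval around 2.0%. This stands as well.

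Two stronger readings are tempting, and the documents support neither:

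- **The loss falls mainly on proximal thrombi.** A reader might infer this because compression cannot be tested in some central veins. The plan does not define proximal and gives no distribution by vein or modality.
- **The thrombotic total is certainly understated.** Some of these DVTs can enter as PE. The fatal PE definition also admits deaths without a documented cause where DVT or PE cannot be excluded, which may raise the total. The net direction of error in the total is not established.

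**Conclusion.** The point holds as a correctable inconsistency in a primary endpoint definition. For venography the section contradicts itself; for CT and MRI it leaves a gap. Read literally, the DVT component can only be undercounted. Read loosely, it is classified inconsistently between physicians.

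The relative loss in DVT incidence equals f, which the documents do not give. The assumed range of 0% to 30%, with N = 500 and 10 true DVTs, is an illustration and not an estimate for this cohort. The effect on total thrombotic incidence is smaller in relative terms once PE is counted, and no figure for it can be derived. The finding does not invalidate the study. It should be settled because the remedy is a change of wording that needs no new tests.

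**What to change.** 1. In both DVT definitions, replace the single finding with alternatives: a (new) DVT objectively documented by compression ultrasound or by venography, matching the evidence the PE criteria already accept; or a (new) filling defect within a deep vein on CT or MRI, parallel to the incidental PE criterion.
2. Separate the incidental PE entry from the symptomatic DVT list so that each item clearly belongs to one event.
3. Record the confirming modality and the vein on the CRF for every DVT.
4. Report the ultrasound-only DVT count and incidence beside the main figure.

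**Cost.** Two reworded definitions, an added CRF entry for modality and vein, and one extra reported count. No new imaging is needed, because any qualifying scan is already in the chart. Counted incidence may rise slightly, and a few false-positive CT or MRI findings may be admitted. The ultrasound-only count makes both effects visible.
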